### LVEF dose modification

### Asymptomatic Decrease in LVEF

The decision to continue or hold STUDY DRUG is based on the ejection fraction as it relates to the institution's LLN and change in ejection fraction from screening (LVEF as measured at registration) according to the following table:

Change in LVEF from Baseline →  Relationship of LVEF to Institution LLN ↓	Decrease < 10%	Decrease 10-15%	Decrease ≥ 16%
Normal	Continue	Continue	Continue And repeat MUGA day 1 next cycle
1-5% below LLN	Continue And repeat MUGA day 1 next cycle	Continue And repeat MUGA day 1 next cycle	HOLD And repeat MUGA in 2 weeks
≥ 6% below LLN	Continue And repeat MUGA day 1 next cycle	HOLD And repeat MUGA in 2 weeks	HOLD And repeat MUGA in 2 weeks

### Discontinue sunitinib if:

- after holding study drug for 2 weeks, the repeat MUGA has not improved to normal or to the levels that allow continuing treatment
- after holding study drug, and restarting it, the LVEF falls again into the "hold" range IF LVEF remains at a "Continue And repeat MUGA" or improves from a HOLD to a "Continue And repeat MUGA" category, additional MUGA scans prior to the next scheduled MUGA will be at the discretion of the investigator.

### Symptomatic Cardiac Events

Discontinue sunitinib if:

- Patient has symptoms of CHF and a diagnosis of CHF is confirmed
- Patient has a myocardial infarction

### 8.3.5 Other Hematologic and Non-hematologic Adverse Events (not specifically addressed above)

**General Management Guidelines** 

General Managem	ent Guidennes
Observation	Action
AE resolves promptly* with supportive care	Maintain dose level

 
Grade 3 or higher (non-haematological) AE related to sunitinib and lasting >5 days that does not resolve to grade 2 or below despite maximum supportive care for ≤ 48 hours.
 
Lower grade but related AEs (e.g., creatinine)
 
	Reduce one dose level
AE does not resolve to grade 2 or below after treating patient at the lowest ( i.e. , 25 mg daily) reduced dose level.	In general, remove patient from study

\*Prompt resolution indicates resolution to grade 2 or below.

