#### Sunitinib dose levels\*

Dose Level	Daily Dose
-3	12.5 mg
-2	25 mg
-1	37.5 mg
0	50 mg

\* dispensed using 12.5mg, 25mg and 50mg capsules as applicable

The major toxic effects of sunitinib which may limit dose are: neutropenia, thrombocytopenia, fatigue, hand-foot syndrome, hypertension, and changes in liver enzymes. The guidelines that follow outline dose adjustments for several of these toxic effects. If a patient experiences several adverse events and there are conflicting recommendations, please use the recommended dose adjustment that reduces the dose to the lowest level.

For all dose modifications, please note:

- Cycle length of 6 weeks should be maintained even if doses are missed during the 4 weeks of planned treatment (i.e. treatment interruptions should not re-set the cycle timing such that the next cycle starts earlier and missed doses should not be 'made up' in the observation period during weeks 5 and 6). However, the cycle length may be increased in the event that a new cycle of treatment is delayed.
- Supportive care recommendations for sunitinib-related effects can be found in section 8.1.3.
- Patients requiring more than three dose reductions will be removed from protocol therapy.
- Patients who do not recover from toxic effects as required within 3 weeks will be removed from protocol therapy.
- No dose escalations are permitted after reductions for confirmed toxicity (except for the circumstance as described for QTc prolongation in section 8.3).

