## 16.7 Safety Issues

The most frequent adverse events (AEs) seen following sunitinib treatment are constitutional (fatigue/asthenia), gastrointestinal (nausea, vomiting, diarrhoea, abdominal pain, anorexia, stomatitis, dysgeusia) and hematologic (neutropenia, thrombocytopenia) as well as skin discoloration (Investigator's Brochure SU011248, 2008). Most of the AEs are grade 1 or 2, but at 75 mg daily on an early phase I trial, grade 3 and 4 fatigue/asthenia were dose-limiting but readily reversible on discontinuation of treatment (Rosen 2003). These investigators noted that the frequency and severity of AEs appeared to correlate with higher drug exposure or with lower performance status of the patients. In another phase I study, grade 3 fatigue and hypertension were dose limiting at 59 mg/m2 and the MTD was defined as 42 mg/m2 daily (Raymond 2003). Tumour responses in patients treated at higher doses on this study were often associated with reduced intratumoral vascularization and central tumour necrosis which led to organ perforation in one patient and fistula in another. These observations indicate the necessity for careful tumour density monitoring to detect early evidence of necrosis. Rapid destruction of bulky solid tumours can occur following sunitinib treatment, with pneumothorax, intestinal fistulae, or intestinal perforation each occurring at an incidence of less than 1.5% of patients. Across all patient populations, fatigue, hematologic AEs, and lipase elevations were the most common grade 3 and 4 events.

In addition to the frequent AEs noted above and those which are infrequent but severe, the following events have occurred: grade 2 edema and oral ulceration in AML (Fiedler 2005); transient grade 3 and 4 hypertension, asymptomatic lipase increases (with or without amylase elevations), skin irritation in imatinib-resistant GIST (Desai et al., 2004); and grade 3/4 glossodynia in the NET trial (Kulke 2005).

Additional reports from the manufacturer include anemia, pyrexia, and dyspnea in AML; and abdominal pain, dyspepsia, skin discoloration, headache, constipation, dermatitis, increased lipase, limb pain, and taste disturbance in various solid tumour patients (Investigator's Brochure SU011248, 2008). Of interest, dyspepsia, dysgeusia, and stomatitis were reported twice as often in MRCC as in GIST, although these events occurred in both populations.

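### The residual dose-reduction table in Section 8.3.5 is inconsistent in its grade 3+ trigger, its handling of low-grade events and its lowest dose level, so sites could dose the same event differently

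*Combined protocol and SAP*

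**What the plan says.** Section 8.3 of the combined protocol and SAP gives specific rules for hypertension (8.3.1, 8.3.2), neutropenia and thrombocytopenia (8.3.3) and a list of other toxicities (8.3.4). Section 8.3.5 takes the rest. Its table, headed General Management Guidelines, has three rows:

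- **Maintain the dose level.** The condition is "AE resolves promptly* with supportive care". The footnote adds "Prompt resolution indicates resolution to grade 2 or below" and sets no time limit.
- **Reduce one dose level**, under either of two items. Item 1 is a related, non-haematological event of grade 3 or higher, lasting more than 5 days, that "does not resolve to grade 2 or below despite maximum supportive care for ≤ 48 hours". Item 2 reads "Lower grade but related AEs (e.g., creatinine" and, apart from closing that bracket, adds no grade, duration or non-resolution condition.
- **In general, remove the patient.** This applies when an event stays above grade 2 at the lowest reduced level, which the row gives as 25 mg daily.

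Section 8.3 lists four daily doses: 50, 37.5, 25 and 12.5 mg (levels 0 to -3). For several adverse events with conflicting recommendations its instruction is "please use the recommended dose adjustment that reduces the dose to the lowest level". It bars escalation after a reduction for confirmed toxicity, except for QTc prolongation. It removes patients who need more than three reductions, and those who have not recovered as required within 3 weeks.

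**The concern.** A residual table should give one action for each event that reaches it. Here the grade 3+ item can leave out the event that was treated most promptly. The low-grade item can send a mild event to a lasting reduction while another row keeps the dose. The row on removal uses a different lowest dose from the dose-level table. Stomatitis, dysgeusia, lipase elevation and creatinine rise have no row elsewhere in 8.3, so their handling depends on this table.

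Delivered dose, decisions to take patients off treatment and the toxicity picture sought under objective 1.2 could therefore vary with how each of the three centres in Section 5.0 reads it. The safety side matters more than the statistical one: a severe related event could have no instruction in the table at the time it needs one.

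**Working it through.** **1. The grade 3+ trigger.** Inputs, all from Section 8.3.5: event duration D must exceed 5 days, and hours of maximum supportive care C must be 48 or less. For an unresolved event with maximum care begun on day S and continued,

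C = (D − S) × 24, so item 1 is met when D > 5 and (D − S) × 24 ≤ 48, that is, S ≥ D − 2.

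| D (days) | S (day care began) | C (hours) | Item 1 met? |
|---|---|---|---|
| 6 | 0 | 144 | no |
| 6 | 3 | 72 | no |
| 6 | 4 | 48 | yes |
| 6 | 5 | 24 | yes |
| 10 | 0 | 240 | no |
| 10 | 7 | 72 | no |
| 10 | 8 | 48 | yes |

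With care from onset (S = 0), D > 5 forces C > 5 × 24 = 120 hours, which exceeds 48, so item 1 is never met. An event of 5 days or less never meets it either, whenever care began. In both cases the maintain row does not apply, because the event is still above grade 2. The removal row applies only at the lowest dose, so above that dose the table assigns no action. By contrast, 8.3.3 and 8.3.4 give an explicit action for grade 3 and 4 neutropenia, thrombocytopenia, fatigue, hand-foot syndrome and AST/ALT elevation.

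**2. Events at grade 2 or below.** Take a related grade 1 or 2 event.

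| Supportive care given? | Maintain row | Reduce row, item 2 |
|---|---|---|
| Yes | can be read as met (at grade 2 or below, no time limit) | met |
| No | not met | met |

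With supportive care, both rows can be read to apply. The tie-break in Section 8.3 does not clearly settle this, since it is worded for several events and not for one event that fits two rows. For the five toxicities named in step 1, grades 1 and 2 mean no dose change. The CPK row does act at grade 2, so that pattern is not universal.

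**3. The lowest level.** Section 8.3.5 puts it at 25 mg, which is level -2, reached after two one-level reductions from 50 mg. Section 8.3 goes to level -3, 12.5 mg, reached after three, and removes patients only beyond three. An unresolved event at 25 mg therefore generally means removal under one section, while the other still lists a lower level.

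**4. What a level is worth.** Four weeks of daily dosing is 28 doses per cycle.

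| Level | Dose per cycle | Share of planned dose |
|---|---|---|
| 0 | 28 × 50 = 1400 mg | 100% |
| -1 | 28 × 37.5 = 1050 mg | 75% |
| -2 | 28 × 25 = 700 mg | 50% |
| -3 | 28 × 12.5 = 350 mg | 25% |

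One low-grade event read into the reduce row instead of the maintain row changes planned dose from 1400 to 1050 mg per cycle.

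**The case against.** Several points on the other side stand.

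- A reader might infer that the grade 3+ trigger can never be met. It can: the first table shows that care started late satisfies it. The wording is misdirected and leaves a gap, but it is not impossible to apply.
- The 48 hours might be read as a window of care already completed before day 5. That would bring in events treated from onset. The sentence does not say so, and on that reading the 48-hour limit would exclude almost nothing once some maximum care had been given.
- This part turns on one inequality sign, which should be checked against the source document. If the sign differs, the first table must be redone. The lack of any action up to day 5 and parts 2 and 3 would remain.
- A reader might infer that a persistent grade 3 or 4 event stays at full dose without limit. It does not: Section 8.3 removes patients who have not recovered within 3 weeks, and Section 12.1 allows discontinuation for unacceptable toxicity. The note after the 8.3.4 table speaks instead of delays beyond 4 weeks and allows discretion, so this backstop is not uniform, but it exists.
- Resolving to grade 2 may presuppose a start at grade 3 or above. The two rows then do not overlap, but item 2 would reduce the dose for every related low-grade event. The text states neither reading.
- Section 16.7 says "Most of the AEs are grade 1 or 2", and a reader might infer that 8.3.5 decides dose for most patients. The same paragraph's frequent events include fatigue, neutropenia and thrombocytopenia, which have their own rows. Nausea and diarrhoea also have supportive-care sequences in 8.1.3.
- A reader might expect bias in a reported dose-reduction rate. Neither objective 1.2 nor the secondary endpoints in Section 11.2 names such a rate.

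**Conclusion.** The point holds in this limited form: Section 8.3.5 is internally inconsistent as a residual dosing rule. Read literally, it leaves out related grade 3+ events given maximum care from onset, allows a related grade 1 or 2 event under supportive care to be read into two opposite actions, and disagrees with Section 8.3 on the lowest dose. These are operative instructions with safety consequences, so the wording is a defect and not merely thin detail.

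The size per decision is one dose level, 25 percentage points of planned dose, generally not reversible under Section 8.3. How many patients would be affected cannot be derived, because the documents give no frequency for events reaching this table. Any effect on observed activity through delivered dose is therefore unquantified. Alpha, power and sample size in Section 11.3 do not depend on it. The conclusion assumes a literal reading, continuous maximum care once started and, for the 48-hour condition, that the inequality sign is as printed.

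**What to change.** First check the inequality sign in item 1 against the source document. Then the sponsor should reconcile three things, so that each event falls under one action:

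1. the two time conditions in the grade 3+ item, including what applies before they are met;
2. the maintain and reduce rows for events at grade 2 or below;
3. the lowest dose level in 8.3.5 with the dose-level table in 8.3.

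The clinical values and rules are the sponsor's to choose, and none is proposed here. The cost is an amendment to one short table, through the Health Canada and REB review that Section 15.3 already requires, and a note to the three centres. No patients, visits or tests are added.

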### **8.4 Concomitant Therapy**

#### 8.4.1 Permitted

Patients may receive ongoing supportive and palliative care (eg. pain control) as clinically indicated throughout the study. All supportive medications must be recorded on the case report form (CRF) as appropriate.

#### 8.4.2 Not permitted

The case report form (CRF) must capture the concurrent use of all other drugs, over-the-counter medications, or alternative therapies including herbal supplements, specifically, St. John's wort (which is not permitted). The Principal Investigator should be alerted if the patient is taking any agent known to affect or with the potential to affect selected P450 isoenzymes. (A comprehensive list of CYP3A4-interactive agents is provided in Appendix VI.) If any of the prohibited concomitant medications become necessary for patient management, please contact the pharmacy for discussion about appropriate washout periods and possible drug interactions.

Cytochrome P450 inhibitors, substrates or inducers:

• Sunitinib is primarily metabolized by liver enzymes, particularly CYP3A4. Co-administration of potent inhibitors or inducers of this enzyme can result in significant changes in exposure to sunitinib (e.g., a mean 1.8-fold increased exposure with ketoconazole and a mean 4-fold decrease with rifampin). For this reason, use of the following agents is not permitted before or during the study:

Inhibitors/substrates – prohibited 7 days before dosing and during study	Inducers/substrates – prohibited 12 days before dosing and during study.
azole antifungals (ketoconazole, itraconazole, miconazole, voriconazole)	rifampin
HIV protease inhibitors (indinavir, saquinavir, ritonavir, atazanavir, nelfinavir)	Anti-convulsants: carbamazepine, phenytoin
Macrolide Antibiotics: clarithromycin, erythromycin, telithromycin	rifabutin
Non-dihydropyridine calcium channel blockers: diltiazem verapamil	
	St. John's wort
delavirdine	
	HIV antivirals: efavirenz, nevirapine
grapefruit juice	phenobarbital
	tipranavir

A comprehensive list of CYP3A4 inhibitors, inducers, and substrates is provided in Appendix VI.

### Steroids:

• Steroid use is not recommended during sunitinib treatment unless absolutely necessary (e.g., for treatment of adverse events or protocol-required premedication) because many steroids (e.g., prednisone, prednisolone, dexamethasone, etc) effectively lower sunitinib exposure through CYP3A4 interactions.

#### Anticoagulants:

• The use of coumadin-derivative anticoagulants such as warfarin (Coumadin®) in therapeutic doses is not permitted, although doses of up to 2 mg daily are permitted for prophylaxis of thrombosis. Low molecular weight heparin is permitted provided the patient's INR is < 1.5.

### Dysrythmic drugs:

• Use of agents with proarrhythmic potential (amiodarone, terfenadine, quinidine, procainamide, disopyramide, dofetilide, dronedarone, ibutilide, sotalol, probucol, bepridil, haloperidol, risperidone, indapamide, and flecainide) is not permitted during the study. A comprehensive list of agents with proarrhythmic potential can be found at http://crediblemeds.org.

### 9.0 EVALUATION DURING AND AFTER PROTOCOL TREATMENT

### 9.1 Evaluation During Protocol Treatment

Investigation	Timing	Investigation	Timing
History and Physical Exam	Day 1 each cycle 	CBC, differential	Day 1 each cycle (prior to treatment) 
Weight, performance status 	Day 1  , 15, and 29 each cycle	PT/INR/PTT 	Twice weekly for first 3 weeks, then as clinically indicated
Clinical tumour measurements	End of every even numbered cycles	Biochemistry	Day 1 each cycle 
Blood pressure, heart rate 	Weekly for cycle 1  then Day 1  , 15, and 29 each cycle thereafter (assessed by nurse or home monitor)	BUN, serum creatinine/clearance  , sodium, potassium, chloride, bicarbonate, bilirubin, alkaline phosphatase, AST, ALT, LDH, total protein, calcium, phosphate, albumin, glucose, CPK	Day 1 each cycle 
Adverse Events/ Toxicity Evaluation 	Each visit at the end of every cycle	Amylase, Lipase	Day 1 each cycle 
Urinalysis	Day 1 each cycle 	TSH, T4	Day 1 each cycle 
EKG	Day 1 of even numbered cycles 	LVEF  / MUGA	Day 1 of even numbered cycles 
Endocrine testing (urinary metanephrines, catecholamines and serum chromogranin A)	Day 1, every 2 cycles 	CXR or CT 	End of even numbered cycles

Each visit:

 $^{1}$  Repeat daily if BP > 150/100 mmHg if previously WNL, OR recurrent, persistent (> 24Hrs) or symptomatic increase by > 20 mmHg and manage as per Section 8.3.

<sup>2 Only for patients receiving low dose anticoagulants (< 2 mg coumadin, warfarin) or LMW heparin.

 $^{3}$  Only required if serum creatinine is > ULN. Creatinine clearance to be measured directly by 24 hour urine sampling or as calculated by Cockcroft Formula: GFR = 1.04 x (140-age) x weight in kg NB: this version of the formula incorporates a 15% reduction for women

<sup>4 To ensure comparability, baseline xrays/scans/LVEF and subsequent xrays/scans/LVEF to assess response and cardiac effects must be performed using identical techniques.

<sup>5 Adverse events will be recorded and graded using NCI Common Terminology Criteria for Adverse Events Version 3.0 (CTCAE) (Appendix IV)

<sup>6 LVEF required in patients with class II NYHA, prior anthracyclines or prior central thoracic radiation, and at investigator's discretion in patients without cardiac risk factors. Identical technique must be used throughout.

<sup>7 Excluding cycle 1

<sup>8 Can be once per cycle at physician's discretion for cycle 3+

<sup>9 Weekly for cycle 1 then day 1, 15, 29 for cycle 2-3, then can be once per cycle at physician's discretion. Repeat daily if BP > 150/100mm HG if previously within normal limits, or recurrent, persistent (>24 hrs) or symptomatic increase > 20 mm Hg and manage as per protocol. Measurements may be performed more frequently at physician's discretion.

<sup>10 Measurements do not have to be repeated cycle 1 Day 1, if screening visit occurred  $\leq$  3 days prior.

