### ON TREATMENT EVALUATIONS

Day 1 each cycle (within 7 days prior to treatment)

- Physical exam (weight, ECOG PS, vital signs)
- Hematology, biochemistry, urinalysis, TSH, T4
- Toxicity assessment

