### Weekly, Cycle 1, then every 2 weeks, cycle 2+

• Blood pressure and heart rate (by nurse or home monitor)

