### 8.2 Patient Monitoring

#### Blood pressure

Patients should have blood pressure determined weekly for the first cycle of therapy and then at least every two weeks thereafter (see Appendix VII). More frequent blood pressure assessment will be required should hypertension be documented: BP should be repeated daily if BP rises to >150/100 if previously normal or if there is a recurrent persistent (>24 h) increase of >20 mmHg. Management is outlined in section 7.3. Blood pressure data should be recorded as appropriate on the CRFs.

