## APPENDIX I – STUDY CALENDER

APPENDIX I	Pre-							Off						
	Study 11	Wk 116	Wk 2	Wk 3	Wk 4	Wk 5	Wk 6	Wk 7 	Wk 8	Wk 9	Wk 10	Wk 11	Wk 12	Stu dy 
Informed Consent	X		_					,						
Demographics	X													
Medical History	X													
Concurrent Meds	X	X											X	
Physical Exam 	X	X						X						X
Height	X													
Weight 	X	X		X		X		X		X		X		X
Performance Status 	X	X		X		X		X		X		X		X
Urine Pregnancy Test 	X													
CBC w/diff, platelets	X							$X^8$						
PT/INR/PTT 	X	Tw	ice a w	eek				As cli	nically	indicat	ed			
Chemistry 	X							$X^8$						X
TSH, T4, Amylase, Lipase	X							X						
Urinalysis	X							X						
BP and HR measurement 	X	X	X	X	X	X	X	X		X		X		X
EKG	$X^{13}$							$X^9$						
LVEF-MUGA 	$X^{13}$							$X^9$						
Endocrine testing	X							$X^9$						
Primary archival tissue block	X													
Adverse Event evaluation 	Base- line sympto ms	X			•••••					•••••			X	X
Clinical tumour measurement	X	Docu	Repeated every 12 weeks (2 cycles). 15 Documentation (radiologic) must be provided for patients removed from study for progressive disease.					$X^{10}$						
Radiologic evaluation	$X^{14}$								$X^{10}$					

<sup>1 Can be once per cycle at physician's discretion for cycle 3+
 Only for women of childbearing potential
 Only for patients receiving low dose anticoagulants or LNW heparin

 Weekly for cycle 1 then day 1, 15, 29 for cycle 2-3, then can be once per cycle at physician's discretion. Repeat daily if BP > 150/100mm HG if previously within normal limits, or recurrent, persistent (>24 hrs) or symptomatic increase > 20 mm Hg and manage as per protocol. Measurements may be performed more frequently at physician's discretion.

LVEF measurements necessary for patients with class 2 NYHA, piror anthracycline or central thoracic radiation, and at investigator's discretion in patients without cardiac risk factors

Adverse events will be recorded and graded using NCI Common Terminology Criteria for Adverse Events version 3 (CTCAE)

Hematology and biochemistry should be repeated day 1 each cycle prior to sunitinib treatment

EKG, MUGA, endocrine testing (urinary metanephrines, catecholamines, serum chromogranin A) should be repeated on day 1, every two cycles.

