#### APPENDIX VII - COLLECTION/RECORDING OF BLOOD PRESSURE INFORMATION

#### 1 0 General Guidelines

## 1.1 Frequency of Monitoring

Blood pressure (BP) should be monitored weekly during the first cycle of sunitinib therapy, then at least every 2 weeks for the duration of treatment.

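### From cycle 4 two footnotes let blood pressure drop to once per cycle with no day named, so a reading during dosing is no longer assured, while three other places still ask for one every two weeks

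*Combined protocol and SAP*

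**What the plan says.** Three places set a two-weekly rule with no exception of their own:

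- The Trial Summary (On Treatment Evaluations) heads its BP line "Weekly, Cycle 1, then every 2 weeks, cycle 2", followed by a plus sign, meaning cycle 2 onward.
- Section 8.2: "Patients should have blood pressure determined weekly for the first cycle of therapy and then at least every two weeks thereafter".
- Appendix VII, 1.1: weekly in the first cycle, "then at least every 2 weeks for the duration of treatment".

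The two operative schedules are looser. The BP row of the section 9.1 table gives Day 1, "15, and 29 each cycle thereafter (assessed by nurse or home monitor"), but footnote 9 to that row reads "Weekly for cycle 1 then day 1, 15, 29 for cycle 2-3, then can be once per cycle at physician's discretion". Appendix I footnote 5 has the same clause: "then can be once per cycle at physician's discretion". Neither footnote says on which day the single reading should fall. Footnote 9 also permits extra readings.

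Two other provisions bear on this. The Trial Summary lists "Physical exam (weight, ECOG PS, vital signs") under "Day 1 each cycle (within 7 days prior to treatment"), so one set of vital signs per cycle is taken before dosing starts. Weight and performance status are due every two weeks (Trial Summary; Days 1, 15 and 29 in section 9.1), but section 9.1 footnote 8 lets the physician reduce them to once per cycle from cycle 3.

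**The concern.** There are two linked problems. First, the general text and the schedule footnotes give different minimum frequencies from cycle 4, and nothing says which governs. One site could take three readings per cycle and another one, and each could claim to follow the protocol.

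Second, the footnotes leave the day open. One pre-dose reading per cycle is already collected with the Day 1 examination, and it can satisfy the relaxed rule by itself. That reading falls in the rest weeks, although the purpose of monitoring is to see BP while the patient takes sunitinib. Section 8.3 names hypertension among the effects that may limit dose, and Appendix VII 1.3 lists endocrine conditions among the risk factors for it. The hold and reduce rules in section 8.3.1 act on a measured value, so an asymptomatic rise during dosing triggers nothing unless someone takes a reading then.

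**Working it through.** The plan states no figure for this point, so the check is a count of scheduled readings.

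**Inputs.** A cycle is 42 days, 28 on drug and 14 off (section 8.1). Day 1 assessments may be up to 7 days early (Trial Summary; section 9.1 footnote 11; Appendix I footnote 16). Stable patients have a maximum of 6 cycles (section 12.2). Half-lives are about 40 hours for sunitinib and 80 hours for its main metabolite (section 16.6). Vital signs are taken to include BP; Appendix VII 3.1, which records BP at each clinic visit, supports this.

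**When the Day 1 reading falls.** The last dose is on day 28 and the next Day 1 is day 43. With the 7-day window the earliest date is day 43 − 7 = 36. Time since last dose is therefore 36 − 28 = 8 to 43 − 28 = 15 days.

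**Drug remaining at that reading**, as 0.5^(hours since last dose ÷ half-life), assuming simple exponential decline:

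- 8 days = 192 h: parent 0.5^4.8 ≈ 4%; metabolite 0.5^2.4 ≈ 19%.
- 15 days = 360 h: parent 0.5^9 ≈ 0.2%; metabolite 0.5^4.5 ≈ 4%.
- Day 29, for comparison, 24 h: parent 0.5^0.6 ≈ 66%; metabolite 0.5^0.3 ≈ 81%.

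Day 29 is thus close to on-drug exposure, and a Day 1 reading is not. This describes exposure only; it does not show how BP behaves.

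**Counts.** Cycles 1-3 give 6 + 3 + 3 = 12 readings under either rule. For cycles 4-6:

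| | Two-weekly (Days 1, 15, 29) | Footnote minimum met at Day 1 | Proposed (Day 1 plus Day 15 or 29) |
|---|---|---|---|
| Readings, cycles 4-6 | 3 × 3 = 9 | 3 × 1 = 3 | 3 × 2 = 6 |
| Total over 6 cycles | 12 + 9 = 21 | 12 + 3 = 15 | 12 + 6 = 18 |
| Day 15 readings | 3 | 0 | 3 or 0 |
| Day 29 readings | 3 | 0 | 0 or 3 |
| Longest nominal gap | 14 days | 42 days | 42 − 14 = 28 days |

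With the Day 1 window, the 42-day gap becomes 42 ± 7 = 35 to 49 days.

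**Is there another scheduled contact during dosing?** Yes, by default. Weight and performance status are due on Day 15, and if that is a clinic visit, Appendix VII 3.1 requires BP then. The documents do not say where the contact takes place. It disappears only if footnote 8 is used as well. The middle column therefore depends on three choices: using the BP relaxation, meeting it at Day 1, and dropping the Day 15 and Day 29 contacts.

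**The case against.** The relaxation looks deliberate. It stands in both schedules, it is discretionary, and it starts only after 12 scheduled readings. Section 16.6 reports that exposure in cycles 2 and 3 was not above that in cycle 1, and section 8.3 bars dose escalation after reductions apart from the QTc exception, so a physician has grounds for reducing visits in a patient who has been stable. Sections 8.2 and 8.3.2 and footnote 9 already require more frequent checks, or stopping drug, once BP is raised or symptoms appear. All of this stands. It limits the point to patients with no symptoms and no documented hypertension, and it argues for keeping the relaxation. It does not reconcile the three unaligned texts or settle the day.

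A reader might infer more than the documents support, in three ways:

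- *That the section 9.1 table contradicts its own footnote.* It does not; footnote 9 is attached to the BP row and qualifies it. The conflict is with the Trial Summary, section 8.2 and Appendix VII.
- *That using the BP relaxation alone leaves no reading during dosing.* That overlooks the Day 15 contact described above.
- *That section 8.3.1 shows BP falling when sunitinib is held.* The instruction to hold drug while leaving antihypertensives unchanged appears only in the row for patients on maximal therapy. In the other hold rows treatment is added or increased at the same time. Neither describes a patient without documented hypertension.

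**Conclusion.** The inconsistency is real, and the open day leaves a narrow gap in safety monitoring. In the least favourable permitted combination, no BP reading during dosing is scheduled from cycle 4; the 9 readings of cycles 4-6 become 3, at intervals of about 42 days. This assumes that vital signs include BP, that dosing follows the calendar without delay, and that the patient stops at 6 cycles; a responder treated longer under section 12.2 would spend longer under the relaxed rule.

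It would go too far to say that hypertension will be missed or that the toxicity objective is biased. The documents do not say how often the relaxations would be used, or how BP differs between dosing and rest weeks in these patients, so the effect cannot be sized. The primary endpoint is not touched. Severity: minor, worth correcting because it is cheap.

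**What to change.** Keep once per cycle from cycle 4 as the minimum, but require that reading at Day 15 or Day 29, in addition to the Day 1 vital signs. A home reading should suffice, as the section 9.1 table already allows. Because the notes following the section 8.3.4 tables base holds and reductions on clinic readings, a home value in a section 8.3.1 hold range should lead to a clinic check first. Naming the day also means that BP no longer depends on whether footnote 8 is used.

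Use the same wording in five places: the Trial Summary, section 8.2, section 9.1 footnote 9, Appendix I footnote 5 and Appendix VII 1.1.

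The cost is an amendment to those five texts, about one extra home reading per later cycle compared with Day 1 only (3 over cycles 4-6), and an occasional clinic check.
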